In a recent observational study in LTC facilities ¹² we reported i) a diabetes prevalence of 32.5% with most patients treated with oral antidiabetic drugs (OADs) alone or in combination with sliding scale regular insulin, ii) high frequency (44%) of hypoglycemic events, and iii) residents with hypoglycemia have a longer length of stay, emergency room or hospital transfers, and higher mortality compared to those without hypoglycemia (see preliminary results). In a pilot study in LTC patients with diabetes, we randomized 100 patients with diabetes to receive low-dose basal (glargine) insulin and rapid-acting insulin before meals or to continue OADs (metformin and/or sulfonylurea) plus regular insulin before meals for BG > 200 mg/dl. We observed similar improvement in HbA1c at 3 and 6 months and in the frequency of hypoglycemia (basal 28% vs. control 31%; please see preliminary results). The results of our preliminary studies indicate the need for safe and effective protocols to achieve glucose control with a low rate of hypoglycemia. We propose two strategies that have been shown to improve glucose control with low rates of hypoglycemia in the hospital, which could be easily implemented in LTC facilities ^{13,14}. The 'basal plus' approach with a daily dose of glargine plus correction doses of rapid-acting insulin was shown to be as effective as basal bolus regimen in improving glucose control in general medicine and surgery patients with type 2 diabetes (T2D) ¹³. The sitagliptin inpatient trial ¹⁴ reported that treatment with DPP4 inhibitor alone or in combination with insulin glargine results in similar glucose control compared to a basal bolus regimen in inpatients with T2D. No clinical trials have determined the safety and efficacy of basal insulin (standard of care) and DPP4 inhibitors in LTC facilities. *Accordingly, we propose a prospective randomized controlled trial comparing treatment with a DPP4 inhibitor (linagliptin) to a basal plus (glargine) regimen (\pm metformin for both treatments) in LTC residents with T2D.*

Specific Aim and Hypothesis:

Aim 1. To determine whether glycemic control, as measured by change in mean BG, HbA1c and frequency of hypoglycemia, is different between treatment with linagliptin (Tradjenta®) and basal insulin in LTC residents with T2D. Patients with poorly controlled diabetes (HbA1c >7.5%) will be randomized to a 6-month intervention with linagliptin or glargine

insulin (\pm metformin for both treatments).

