Hypothesis: Treatment with linagliptin, a once daily DPP4-inhibitor, will result in similar improvement in glucose control but in a lower rate of hypoglycemia than insulin treatment in LTC residents with T2D.

Aim 2. To determine differences in clinical outcome, resource utilization, and hospitalization costs between LTC residents with T2D treated with linagliptin and basal plus insulin. We will compare differences in complications (infectious and non-infectious, neurological and cardiovascular events), emergency room visits and hospitalizations between groups during the 6 months of intervention.

Hypothesis: Treatment with linagliptin will result in similar number of complications and resource utilization compared to insulin treatment in LTC residents with T2D diabetes.

II. BACKGROUND AND CURRENT STATUS OF WORK IN THE FIELD.

Prevalence of diabetes in the elderly and long-term care facilities. The prevalence of diabetes mellitus increases with age, and it is estimated that more than 20% of older adults aged 65-75 years and 40% of adults >80 years of age have diabetes ^{1,2}. The prevalence of diabetes in the elderly is expected to increase due to longer life expectancy and improve care of the population ^{2,15}. The estimated prevalence of diabetes in LTC facilities is reported to be $\sim 15\%$ to 32% ⁴, and in parallel to the increasing geriatric population, the number of LTC facilities is expected to rise ¹⁵.

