A total of 150 male or female LTC residents with type 2 diabetes with an fasting or random BG >/= 180 mg/dL and/or an A1c > 7.5% while receiving treatment with diet (no pharmacological therapy), OADs (metformin, secretagogues, thiazolidinediones), low dose insulin of 0.1U/kg/day or sliding scale regular insulin will be randomized to receive linagliptin or glargine insulin therapy.

This study will be performed at Crestview, a community LTC institution affiliated with Grady Health System; Budd Terrace on the Wesley Woods campus of Emory University; and the Community Living Center at the Atlanta VA Medical Center, Atlanta.

IV.c. Primary and Secondary Research Outcomes:

[figure not shown]
The primary endpoint of the study is change in mean BG over a 6-month treatment period between treatment with basal plus insulin regimen and aDPP4 inhibitor in LTC residents with poorly controlled diabetes.

Secondary outcomes include differences between treatment groups in any of the following measures:

1. Percentage of HbA1c ≤ 7.5% at 3 or 6 month independent of the occurrence of hypoglycemia.
2. Occurrence rate and total number of hypoglycemic events (<70 mg/dl) and severe hypoglycemia (< 40 mg/dl).
3. Total daily dose of insulin, metformin and linagliptin.
4. Change in hemoglobin A1c over a 6-month treatment period
5. Changes in cognitive function assessed by mini-mental examination.
6. Prevalence of acute complications (urinary tract infections, pneumonia), bedsores, diabetic foot infection.
7. Need for emergency room visits or hospitalizations during the study period.
8. Cardiac complications are defined as myocardial infarction, cardiac arrhythmia and heart failure.
9. Acute renal failure defined as a clinical diagnosis of acute renal failure with documented new-onset abnormal renal function (increment > 0.5 mg/dL from baseline).

10. Hospital mortality. Mortality is defined as death occurring during admission.

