 - a. Number of patients receiving supplements and dosage as well as metformin therapy.
 - b. Protocol adherence by LTC facility
3. Clinical Outcome (see Aim 2):
 - a. Hospital readmissions, emergency room visits, infectious and non-infectious complications

V. Aim 2. To determine differences in clinical outcome and resource utilization between treatment with linagliptin and basal insulin in LTC residents with T2D.

Rationale. Benefits of improved glucose control on clinical outcomes and hospitalization costs in elderly residents in LTC facilities have not been determined in prospective RCT. This study will compare differences in complications (infections and non-infection, neurological and cardiovascular), resource utilization and hospitalization costs between basal insulin or with linagliptin therapy. We expect that patients treated with basal insulin may have lower daily glucose and HbA1c levels, but higher number of hypoglycemic events. It is not clear if the lower glucose and HbA1c levels will reduce complications, resource utilization and costs compared to patients treated with DPP4 inhibitors who may experience less glucose control but lower hypoglycemic events.

V.a. Data collection and data entry. Baseline and daily information will be entered by the study coordinators into data collection paper forms and into an electronic database (RedCap) provided by the Emory Research Information Technology Department. Baseline data will include demographics/history form (subject gender, age, ethnicity, type of treatment and comorbid conditions, body weight, BMI, laboratory results). Daily information will be collected on treatment, nutrition, blood glucose and laboratory values, hospital complications and adverse events (hypoglycemia).

V.b. Resource utilization. We will prospectively collect information on emergency room visits and hospitalizations, laboratory, pharmacy, consultation services and radiology services, as well as presence of complications including pneumonia, acute myocardial infarction, heart failure, acute renal failure, wound infections and bedsores, cerebrovascular events, and other complications.

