V.c. Financial assessment. The Analytic Information Warehouse (AIW) infrastructure program will be utilized to support extraction, mapping and modeling of electronic health record information from Grady and Emory health records and billing systems. The AIW infrastructure is designed to allow analysts to transform heterogeneous sets of variables into systematically defined core set of data elements. Data will be collected prospectively and also extracted for each patient using ICD-9 codes for demographics, complications, and use of resources including laboratory, radiology, and pharmacy utilizations as well as total charges during the study period. Differences will be expressed by applying Medicare Cost Report cost-to-charge ratios to the charge data using Medicare Hospital Cost Report publish by the Centers of Medicare and Medicaid Services (CMS) (https://wwws.gov/CostReports/02_HospitalCostReport.asp). Based on CMS review of Emory

Long Term Care facilities 2012 cost report, the inpatient cost to charge ratio will be 0.421 for patients admitted in 2013. Data set will be queried to allow analysis of complications, laboratory, pharmacy, consultation services and radiology costs.

V.d. Assessment and Monitoring of Nosocomial Infections. Nosocomial infections will be diagnosed based on standardized CDC criteria ⁵⁹. New infections will not be diagnosed until 48 hr after study initiation to minimize the chance that the infection was actually present prior to study initiation.

V.e. Monitoring of renal function. Acute renal failure is defined as an increment > 0.5 mg/dl from baseline.

V.f. Cerebrovascular accident. Defined as neurologic deficit persisting > 72 hr, transient ischemic attack, deficit resolving within 24 hours, or deficit lasting > 24 - < 72 h (reversible ischemic neurologic deficit).

V.g. Major Cardiovascular Events (MACE). All outcome data will be defined per standard American College of Cardiology–American Heart Association definitions:

- Acute myocardial infarction: (1) increase in troponin and creatine kinase (MB) markers with at least one of the following: (a) ischemic symptoms, (b) development of pathologic Q waves on EKG, (c) electrocardiographic changes indicative of ischemia (ST-segment elevation or depression), or (d) coronary artery intervention (e.g., coronary angioplasty) ⁶⁰.
- Congestive heart failure on chest radiograph and with appropriate clinical symptoms/signs ⁶⁰.

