VIII.a. Sample Size and Power Calculations: This study is randomized, open-label controlled trial. The primary endpoint in this study is glycemic control measured change determined by mean daily blood glucose concentrations and in HbA1c at 3 and 6 months of intervention. The median stay at all facilities was 48.9 ± 50 days, therefore the study did not have power to determine a statistical change in glycated hemoglobin at 6 months. The primary endpoint of the study was modified to evaluate the difference between treatment with basal insulin and linagliptin on glycemic control determined by mean daily blood glucose concentrations during LTC stay, as previously reported (62). Main secondary endpoints included differences in the frequency of hypoglycemia, fasting glucose, HbA1c at 3 and 6 months of intervention, complications, emergency room visits and hospitalizations. We made the comparisons using non-parametric Wilcoxon tests for continuous variables and χ^2 tests (or Fisher's exact test) for discrete variables. We summarize demographics, baseline clinical characteristics, and clinical outcomes by the two treatment groups. Data is presented as mean \pm standard deviation for continuous variables and present count (percentage) for categorical variables. Glycemic variability was calculated by standard deviation (SD) of glucose values during entire study and by the mean daily delta (Δ) daily range of blood glucose (daily max – daily min- mum)(20, 24).The data were presented as mean (SD) for continuous variables and count (percentage) for discrete variables unless specified otherwise. We performed statistical analyses with SAS version 9.3.

VIII.b. Analysis of Primary Endpoint:

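### Aim 2 events are promised over 6 months, but stays run about 49 days; no passage says whether events are sought after discharge or failure, and no analysis mentions time at risk

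*Combined protocol and SAP*

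**What the plan says.** **Duration.** Under Specific Aim and Hypothesis, Aim 1 says that patients "will be randomized to a 6-month intervention with linagliptin or glargine", and Aim 2 counts complications, "emergency room visits and hospitalizations between groups during the 6 months of intervention".

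**Outcome list.** IV.c item 7 reads "Need for emergency room visits or hospitalizations during the study period". Item 6, "Prevalence of acute complications (urinary tract infections, pneumonia), bedsores, diabetic foot infection", has no window. Item 10 has its own: "Mortality is defined as death occurring during admission". For the cost outcome, V.c extracts resource use "as well as total charges during the study period". The study period is not defined in any section.

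**Stay.** VIII.a states: "The median stay at all facilities was 48.9 ± 50 days". It concludes that a 6-month change in glycated haemoglobin could not be powered and changes the primary endpoint to mean daily glucose during the LTC stay. Complications, emergency room visits and hospitalisations stay on its list of main secondary endpoints, with no window of their own.

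**End of observation.** IV.g item 4 and section X discontinue residents from the study for persistent hyperglycaemia. Neither says whether events are recorded afterwards. The only timing given relative to discharge is for HbA1c, in IV.i.

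**Analysis.** VIII.c sends discrete Aim 2 outcomes to the approach set out for hypoglycaemia: chi-square or Fisher's exact test, Cochran-Mantel-Haenszel by centre, then logistic and Poisson or negative binomial regression. It mentions no days at risk and no offset.

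**The concern.** The observation problem that led to a new window for the primary endpoint applies equally to Aim 2, where nothing was changed. If residents typically leave well before 6 months, either events are sought after they leave, which needs a stated method, or they are not, and the 6-month statement in Aim 2 cannot be met.

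In the second case follow-up varies from days to 6 months. An analysis that ignores time at risk treats a resident seen for 10 days without an event like one seen for 180 days without an event. Two things follow. Events are lost, and with no equivalence margin given for these outcomes, a non-significant difference between two sparse arms can be read as the similar number of complications and similar resource use that Aim 2 hypothesises. Also, if one arm is observed for less time, for example because more of its residents are discontinued for failure, it will show fewer events for that reason alone.

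**Working it through.** The plan gives no figure for this window, so there is none to reproduce. The check compares the stated stay with the stated window and then asks what the planned models estimate.

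**1. Share of the window covered by the stated stay.** Inputs: 48.9 days (VIII.a) and 6 months (Aim 2), taken as 365.25/2 = 182.6 days.
- 48.9 / 182.6 = 0.268, about 27%.
- 182.6 − 48.9 = 133.7 days.

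A resident who leaves on day 49 therefore has about 134 days in which an emergency visit counts if the window is 6 calendar months and does not count if it is the stay. If 48.9 is a true median, at least half of residents have that many uncertain days or more.

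**2. Share of person-time.** The documents give no distribution of stay, and 48.9 ± 50 is labelled a median but written like a mean and SD. Both readings are therefore shown, with stay counted from randomisation. Mean in-facility days within the window W = 182.6 is the integral of the survival function S(t) from 0 to W. For an exponential stay with mean μ this is μ(1 − exp(−W/μ)).

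| Assumed stay | Stay the full 6 months | Mean days within 6 months | Share of window |
|---|---|---|---|
| Exponential, median 48.9 (μ = 48.9/ln 2) | 7.5% | 65.2 | 36% |
| Exponential, mean 48.9 | 2.4% | 47.7 | 26% |
| Gamma, mean 48.9, SD 50 | 2.6% | 47.6 | 26% |
| Lognormal, mean 48.9, SD 50 | 2.4% | 47.0 | 26% |

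Under these assumptions the stay covers 26–36% of the 6-month person-time, so 64–74% of it depends on which window is meant.

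**3. What a count model without an offset estimates.** Let an arm have event rate λ per day and mean observed days D. Expected events per resident are λ × D. The ratio between arms from a model without an offset is then

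(λ_lina / λ_glar) × (D_lina / D_glar).

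It equals the rate ratio only if mean observed time is the same in both arms. With log(days at risk) as offset, the second factor drops out. Chi-square, Fisher, Cochran-Mantel-Haenszel and logistic analyses have the same dependence, because the chance of at least one event rises with days observed.

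**4. Can equal observation be assumed?** The documents do not show it. Residents discontinued for persistent hyperglycaemia leave the study, and the Aim 2 rationale in section V says that linagliptin may give less glucose control. If event collection stops at discontinuation, the two arms could lose time at different rates.

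**The case against.** The strongest defence is that the study period in IV.c most naturally means the 6-month treatment period. Every duration attached to treatment is 6 months, VIII.a changes only the primary endpoint, and HbA1c at 3 and 6 months stays among the secondary endpoints. This largely stands: Aim 2 and IV.c need not contradict each other, and for complications in IV.c the window is missing, not conflicting. A reader might infer that VIII.a moved the Aim 2 events to the LTC stay, but no passage says so. What the defence does not supply is how events are found for a resident who left at about 49 days or was discontinued.

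It is also fair to say that VIII.c goes beyond crude proportions, since it includes count models and covariate adjustment. The gap is narrower: none of these analyses is said to account for time at risk.

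A reader might go further and compute lost events or lost power from the 44% versus 30% transfer rates in the preliminary cohort (section III). The documents do not support that. Those rates compare residents with and without hypoglycaemia, not linagliptin with glargine. They are not stated to be 6-month risks, and they may already be risks over the stay.

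Nor does the wording in IV.i, "Hospital readmissions, emergency room visits, infectious and non-infectious complications", define a different outcome. That item refers back to Aim 2, and V.b again speaks of hospitalisations.

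**Conclusion.** The point holds as a gap in the definition and analysis of the Aim 2 event outcomes. The plan promises 6 months, reports a stay of about 27% of that, re-cuts only the primary endpoint, and neither says how later events are ascertained nor allows for unequal observation time.

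The firm numbers are 27% of the window and about 134 days for a resident who leaves at the stated figure. The 64–74% of person-time in question rests on assumed stay distributions and on stays counted from randomisation. The effect on event rates or power cannot be computed from the documents.

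Losing events makes a finding of no difference more likely, which is the direction that Aim 2 hypothesises. Unequal observation between arms could bias the comparison either way. The outcomes are secondary, and no stated trial figure changes.

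**What to change.** State one window for all Aim 2 outcomes, in the same words, in Aim 2, IV.c items 6–9, IV.i, V.c and VIII.c, and say how events after discharge and after discontinuation for failure are handled.

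- **If events can be ascertained after discharge at all three sites:** use randomisation to 6 months regardless of discharge or treatment discontinuation. Name a data source for the VA site, because V.c lists only Grady and Emory records and billing systems. The cost is record retrieval after discharge, with equal capture to be secured across sites.
- **If not:** restate Aim 2 as covering observed follow-up or the LTC stay. Say whether a transfer that itself ends the stay counts. Make the main comparison of events a Poisson or negative binomial rate model with log days at risk as offset, and keep the chi-square or Fisher results as description. The cost is one extra model term, a days-at-risk variable and a narrower Aim 2 conclusion.

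In either case, report days observed by arm, with the reasons observation ended, so that a reader can see whether the arms were followed for similar times.

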- **Insulin adjustment.** The total daily insulin dose will be adjusted as follow:
 - Fasting and pre-meal BG between <180 mg/dl without hypoglycemia the previous day: no change
 - Mean fasting and pre-meal BG between 181-280 mg/dl without hypoglycemia: increase glargine dose by 10% every 3 days
 - Mean fasting and pre-meal BG >281 mg/dl without hypoglycemia: increase glargine dose by 20% every 3 days
 - Mean fasting and pre-meal BG between <100 mg/dl: decrease glargine dose by 10% every day
 - If a patient develops hypoglycemia (<70 mg/dL), decrease glargine dose by 20%.
 - If a patient develops hypoglycemia (<40 mg/dL), decrease glargine dose by 30-40%.
- **Blood glucose monitoring.** Blood glucose will be measured before each meal (or every 6 hours if a patient is not eating) using a glucose meter. In addition, blood glucose will be measured at any time if a patient experiences symptoms of hypoglycemia or if requested by the treating physician.

IV.f. Investigational drugs.

1. Linagliptin (Tradjenta®) 5 mg tablets for oral administration. Linagliptin is not a formulary drug at Grady Health System and VAMC and will be provided by Boehringer Ingelheim Pharmaceuticals, Inc (see letter of support, page 76)
2. Glargine insulin: U-100/mL, provided in 10 mL vials. Glargine (Lantus®) is available in all institutions.

IV.g. Withdrawal Criteria

1. The subject may withdraw at any time during the study by primary care provider or research team.
2. The subject may be withdrawn at the investigator's discretion due to a safety concern or if judged non-compliant with trial procedures or for contravention to the inclusion and/or exclusion criteria.
3. Subject diagnosed with acute pancreatitis by clinical and/or radiographic criteria.
4. Patients with severe hyperglycemia defined as 3 consecutive BG levels > 280 mg/dl or 2 consecutive days with an average BG > 280 mg/dL will be considered as failure and discontinued from the study. Patients receiving linagliptin therapy will be switched to basal plus insulin and those on basal insulin will be switched to basal bolus insulin regimen.

IV.h. Subject Replacement

There will be no replacement of subjects in this trial.

IV.i. During follow up we will collect the following information

1. Glycemic control:
 - a. Mean daily fasting and premeal blood glucose levels.
 - b. HbA1c at baseline, 3 and 6 months of discharge
 - c. Number of hypoglycemic events
2. Diabetes treatment:

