Hyperglycemia: supplemental insulin will be given before meals to cover for BG >200 mg/dL. Patients with persistent hyperglycemia defined as 3 consecutive BG levels > 280 mg/dL or 2 consecutive daily average >15.5 mmol/L (280 mg/dL) will be considered as failure and will be discontinued from the study. Patients receiving linagliptin will be switched to basal and those on basal will be switched to basal bolus regimen.

Acute renal failure: patients with GFR <45 ml/min will not be treated with metformin.

XI. Data handling and record keeping: Data collection records with personal identifiers will be stored in locked file cabinets. No blood samples will be stored in this study. Access to research will be limited to clinical investigators, research coordinators, and the IRB at Emory University.

XII. Storage and Drug Accountability of Study Medication(s). Linagliptin will be stored and dispensed by the research pharmacy at each institution. Glargine insulin is standard of care and is available at the three participating institutions and will be dispensed by general inpatient pharmacy.

XIII. Randomization and Blinding. This is an open label randomized controlled trial. Patients will be randomized consecutively using a computer generated randomization table provided by [name] at the Emory School of Public Health. The randomization table will be mailed to the research pharmacist at each institution who will be in charge of the randomization and group assignment.

XIV. Informed Consent. Informed consent will be obtained before any trial related procedures including screening procedures. The consent form will follow the IRB guidelines of Emory University. A signed copy of the consent will be provided to the participant and a copy of the consent will be placed in the study office.

XV. Inclusion of women: We anticipate that ~50% of the study subjects will be female.

XVI. Inclusion of minorities: Patients will not be excluded based on race or ethnic origin. We anticipate that half of patients will be African Americans, 10% Hispanics, and the rest Caucasians.

XVII. Inclusion of children: No patients under the age of 18 will be recruited in this study.

XVIII. Financial Conflict of Interests. None of the investigators in this study have any outside activities that may represent a conflict of interest.

XIV. Data Safety Monitoring Plan.

A Data Safety Monitoring Board or Safety Officer has been designated for this study.

[name]
Department of Medicine/Endocrinology

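### Patients who meet the >280 mg/dl rule leave the study and no analysis set keeps them; outcome collection should continue and they should be analysed by assigned arm (minor)

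*Combined protocol and SAP*

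**What the plan says.** - **The rule.** IV.g item 4 says patients meeting the >280 mg/dl criterion "will be considered as failure and discontinued from the study". The next sentence gives their treatment: "Patients receiving linagliptin therapy will be switched to basal plus insulin", with glargine patients moving to basal bolus. Section X repeats the rule: "will be considered as failure and will be discontinued from the study. Patients receiving linagliptin will be switched to basal". IV.g names basal plus as the next regimen for linagliptin patients; X says only basal.
- **Replacement.** IV.h: "There will be no replacement of subjects in this trial".
- **Follow-up.** IV.i lists the data to be collected, including "HbA1c at baseline, 3 and 6 months of discharge", without mentioning patients discontinued under the rule. Aim 2 compares complications, "emergency room visits and hospitalizations between groups during the 6 months of intervention".
- **Analysis.** VIII.a makes the primary endpoint average daily glucose over the facility stay, and VIII.b sets an 18 mg/dl non-inferiority margin. Section VIII gives no analysis set, no rule for readings before or after failure, and no missing-data method. Failure is not among the outcomes in IV.c.
- **Expected control by arm.** The Aim 1 hypothesis is that linagliptin "will result in similar improvement in glucose control but in a lower rate of hypoglycemia". The rationale in section V allows for "patients treated with DPP4 inhibitors who may experience less glucose control but lower hypoglycemic events".

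**The concern.** The trigger for leaving the study is a high value of the primary outcome variable. If the rule is applied as written, later outcomes are missing because of poor control, and more often on linagliptin if section V's expectation is right. The secondary outcomes would then lack the later experience of the worst-controlled patients in each arm. The record extraction in V.c covers complications, resource use and charges from the Grady and Emory systems. It does not list HbA1c or bedside glucose values, and glucose values define hypoglycemia.

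For the primary comparison, the plan does not say whether these patients are kept. Dropping them removes high values, possibly more from the linagliptin arm, which would favour a non-inferiority claim. Keeping all their readings mixes in glucose measured after linagliptin patients have moved to insulin, which answers a different question.

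**Working it through.** **1. The plan's own sample size.** Inputs from VIII.b: margin 18 mg/dl, SD 40, one-sided alpha 0.05, power 80%.

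n per arm = 2(1.645 + 0.842)² × 40² / 18² = 61.1, so 62. With 10% attrition, 62/0.90 gives 69 per arm, or 138 in total. The plan states 64 per arm and 140 in total. It reproduces approximately, without Bonferroni and with 64 read as the number before attrition. The model below therefore uses 70 per arm.

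**2. Assumed model.** The documents give no expected failure rate, so all of this is assumption: 49-day stay, four readings a day, day-to-day SD 20, reading SD 35, and a true difference of 18 mg/dl (linagliptin higher). Failure is three consecutive readings, or two consecutive daily means, above 280. Non-inferiority is declared if the upper one-sided 95% limit is below 18. Each setting has 4,000 simulated trials. The model omits glargine titration, correction insulin and Bonferroni. Both settings put about 20% of linagliptin readings above 200 mg/dl, the ceiling of the <20% in section IX.

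| Between-patient SD / glargine mean | 28 / 140 | 38 / 135 |
|---|---|---|
| Failures, linagliptin / glargine | 1.1% / 0.2% | 2.9% / 1.0% |
| False non-inferiority, no rule | 5.4% | 5.2% |
| Failures dropped | 6.8% | 8.4% |
| Mean difference, failures dropped (mg/dl) | 17.6 | 16.5 |
| One mean per patient up to failure | 5.3% | 5.1% |

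Repeat runs gave 6.7–8.3% with failures dropped and 4.7–5.0% with readings up to failure.

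Number failing, at 75 per arm (IV.e): 75 × (0.011 + 0.002) = 1.0 and 75 × (0.029 + 0.010) = 2.9, so about 1 to 3 of 150.

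**3. Hand check of the shift.** If failures averaged 280 mg/dl and other patients 160, dropping failures would move the difference by (difference in failure proportions) × 120. That is 0.009 × 120 = 1.1 and 0.019 × 120 = 2.3 mg/dl. The simulated shifts are smaller, 0.4 and 1.5, as expected if a failing patient's mean over the stay is below 280.

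**4. Equal control.** With a true difference of 0, failure rates are equal (0.2% in each arm, or 1.0% in each arm). Dropping failures changes the mean difference by less than 0.1 mg/dl.

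**5. Better control, and varying stays.** With 14–15% of linagliptin readings above 200, dropping failures gives 5.6–6.3%, against 4.6–4.9% with no rule. With stays varying (mean 48.9, SD 50 days) at the two tabulated settings, it gives 5.7–6.3%, against 4.2–4.6%.

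**6. Secondary data lost under the literal rule.**
- In-stay HbA1c = 75 × failure rate × share of failures who would have stayed that long. This is about 0.3–1.0 linagliptin patients at 3 months and 0.1–0.4 at 6 months.
- Hypoglycemia after the switch, taking 12% (section X) to 28% (the pilot in section III): 75 × 0.011 × 0.12 = 0.1 to 75 × 0.029 × 0.28 = 0.6 linagliptin patients. Fewer than 75 × 0.05 = 3.75 linagliptin patients are expected to have any.

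The loss is longer only if follow-up runs past discharge, as the HbA1c wording in IV.i may mean.

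**The case against.** The strongest reply is that little is at stake. VIII.a's endpoint is most naturally computed as one mean per patient from the available readings, and in the model that causes no inflation. The modelled settings sit at the ceiling of section IX's expectation; better control or varying stays shrink the effect further. Most residents would leave before 3 months anyway, and VIII.a already concedes a lack of power for HbA1c at 6 months. All of this stands, and it is why the point is minor.

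Naming a next regimen after withdrawal is not in itself a contradiction, since a withdrawal rule may reasonably say what care follows. That also stands. What remains is that a literal reading stops outcome collection and no sentence in section VIII keeps these patients.

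The cited earlier report and the attached safety monitoring plan were not available and may say more. The protocol text does not.

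A reader might infer that the by-day testing mentioned in VIII.b inflates the error rate. A day-49 comparison of patients not yet failed gives 6.0–7.5% without Bonferroni, but only 3.5–4.1% with a correction for just two comparisons. The selection remains; the inflation does not.

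**Conclusion.** The point holds as a minor one. Followed as written, the rule ends outcome collection on the basis of the primary outcome variable, and section VIII has no analysis set that keeps these patients. At the ceiling of the expected control, about 1 to 3 of 150 patients are affected. False non-inferiority at the margin is about 7–8% if they are dropped and about 5% if each contributes one mean up to failure. These figures rest on an assumed model whose omissions have an unknown net effect on differential failure.

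A reader might infer that the plan excludes failures and so biases the trial toward non-inferiority. The documents do not support this: they say neither that failures are excluded nor that they are kept, and bias also requires a true difference in control, which the Aim 1 hypothesis does not expect. Larger figures (10.5% or 19.8% with failures dropped) need worse control than section IX expects and should not be relied on. The direction of any effect on hypoglycemia is not established.

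**What to change.** Leave the clinical failure and switch criteria unchanged.

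- **IV.g and X:** reconcile the two passages, including the differently named next regimen, on which no view is taken here. State that these patients are recorded as treatment failures and that outcome collection continues to the end of the planned observation period.
- **VIII.b:** include all randomised patients with glucose data, failures included, by assigned arm. Make one mean per patient from readings up to failure the primary analysis, with all readings during the stay as a sensitivity analysis.
- **Secondary outcomes:** count them by assigned arm, including after failure, and report the number of failures by arm.
- **If conduct is complete** (VIII.a is largely in the past tense): apply the analysis rule, extract post-failure events from existing records, and report by arm how many failures lack later data.

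The cost is a few more charts to abstract and one extra analysis. The change does not recover 6-month data lost through ordinary discharge.
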